16.1.6 SUPPLEMENTARY ANALYSIS OF PRIMARY EFFICACY VARIABLE

A supplementary analysis will be done on the primary efficacy variable; the MMRM will be completed as described in [Section 16.1.3](#) for the change from baseline to Week 12 in WOMAC pain score, but no adjustment for intercurrent events will be done.

16.2 SECONDARY EFFICACY

The secondary efficacy analysis will be performed for the ITT Set.

16.2.1. KEY SECONDARY EFFICACY VARIABLES AND DERIVATION**16.2.1.1 First Key Secondary Efficacy Variables and Derivation**

The endpoint to address the first Key Secondary Objective is the WOMAC LK3.1 OA (physical function) change from baseline at Week 12 (Visit 8)

The WOMAC physical function score, is derived by summing the sub-scores for the 17 following items, collected in the *Western Ontario and McMaster Universities Osteoarthritis Index* eCRF page taking into account missing observations as described in [section 7.3](#):

Question: How much difficulty have you had:

Noven Pharmaceuticals, Inc.

Protocol HP-5000-US-07

Each item is rated on a scale of 0 to 4, with 0 being none and 4 being extreme. Therefore, the WOMAC physical function score, for a specific visit, will be one of the integer values from 0 to 68 or missing.

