7.3 MISSING DATA

The total and subscale scores of any assessment with more than one item, will be derived from individual items. Any individual missing item in any scale will not be imputed. If one or more items are missing at a visit, then the associated total score or subscale score will be set to missing.

Missing WOMAC scores will be imputed and used in sensitivity analyses of the primary and key secondary efficacy as per [section 16.1.4](#) and [16.1.5](#).

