7.4 MULTIPLICITY ISSUES

For handling multiplicity in this study, a fixed-sequence procedure will be applied for primary and key secondary endpoints, where the order in which the hypotheses are tested is pre-specified as following: (1) WOMAC pain score, (2) WOMAC physical function score, and (3) WOMAC stiffness score. Testing begins with the first hypothesis about WOMAC pain score, and each test is carried out as long as a significant result with a level of significance of $\alpha=0.05$ is observed in all preceding tests. The fixed-sequence procedure controls the family-wise error rate because, for each hypothesis, testing is conditional upon rejecting all hypotheses earlier in the sequence.

All statistical tests of hypotheses in this analysis will be 2-sided with a Type I Error rate of 0.05.

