16.2.2. ANALYSIS OF KEY SECONDARY EFFICACY VARIABLES

The MMRM models for the key secondary efficacy variables will include change from baseline in WOMAC physical function (or stiffness) score as the repeated dependent variable, with effects for treatment (HP-5000 and placebo), visit, treatment-by-visit interaction, and the baseline WOMAC physical function (or stiffness) score as a covariate. Initially an unstructured covariance matrix will be used to model the correlation among repeated measurements within subject.

If the unstructured covariance matrix fails to converge, the same procedure for selection of covariance structures as was specified for the primary efficacy will be done as listed in [section 16.1.3](#). Descriptive and inferential statistics, comparable to those described in [sections 16.1.3 through 16.1.6](#) for the primary efficacy variable will be presented for each of the key secondary efficacy variables.

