16.3 OTHER SECONDARY EFFICACY

Other secondary efficacy analyses will be performed for the ITT Set. For each below secondary efficacy variable, tables will be produced that display descriptive and inferential statistics by visit and treatment group. For continuous change from baseline variables descriptive and inferential statistics, comparable to those described in [section 16.1.3](#) for the primary efficacy variable will be presented. With no adjustment for intercurrent events.

For the secondary variables expressed as proportion of subjects with a response that is categorized as binary a logistic regression model will be used to obtain the point estimate of the odds ratio between treatment groups (HP-5000 and placebo) and the associated 95% confidence interval.

16.3.1 WOMAC LK3.1 OA (PAIN) CHANGE FROM BASELINE AT WEEKS 1, 2, 4, AND 8

The change from baseline will be analyzed using a MMRM analysis. As described in [section](#)

Noven Pharmaceuticals, Inc.
Protocol HP-5000-US-07

[16.1.3](#) for the WOMAC pain score, the same MMRM model will be applied.

A plot of the LS Mean change from baseline by visit will be presented.

16.3.2 WOMAC LK3.1 OA (PHYSICAL FUNCTION) CHANGE FROM BASELINE AT WEEKS 1, 2, 4, AND 8

The change from baseline will be analyzed using a MMRM analysis. As described in [section 16.1.3](#) for the WOMAC physical function score, the same MMRM model will be applied.

A plot of the LS Mean change from baseline by visit will be presented.

16.3.3 WOMAC LK3.1 OA (STIFFNESS) CHANGE FROM BASELINE AT WEEKS 1, 2, 4, AND 8

The change from baseline will be analyzed using a MMRM analysis. As described in [section 16.1.3](#) for the WOMAC stiffness score, the same MMRM model will be applied.

A plot of the LS Mean change from baseline by visit will be presented.

16.3.4 WOMAC LK3.1 OA (COMPOSITE SCORE) CHANGE FROM BASELINE AT WEEKS 1, 2, 4, AND 8

The change from baseline will be analyzed using a MMRM analysis. As described in [section 16.1.3](#) for the WOMAC composite score, the same MMRM model will be applied, with no adjustment for intercurrent events. The WOMAC Composite score is calculated by finding the total of the scores for the 3 subscales, WOMAC pain, WOMAC physical function and WOMAC stiffness, and then dividing by 96. Higher scores on the WOMAC indicate worse pain, stiffness, and functional limitations.

16.3.5 CHANGE FROM BASELINE IN PAIN INTENSITY ASSESSED ON AN 11-POINT NRS AT WEEKS 1, 2, 4, 8, AND 12

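### One blank item out of 17 sets the physical function score, the first key secondary endpoint, to missing for that visit; prorating with a stated minimum of answered items would keep it at little cost.

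*SAP*

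**What the plan says.** SAP 16.2.1.1 defines the first key secondary endpoint as the Week 12 change in WOMAC physical function. The score "is derived by summing the sub-scores for the 17 following items", collected on the WOMAC "eCRF page taking into account missing observations as described in" SAP 7.3. At any visit it "will be one of the integer values from 0 to 68 or missing", so a prorated, non-integer value is not admitted.

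The operative rule is in SAP 7.3: "Any individual missing item in any scale will not be imputed", and "If one or more items are missing at a visit, then the associated total score or subscale score will be set to missing". It covers every multi-item scale: 5 items for pain, 2 for stiffness, 17 for function. It also reaches the composite, because SAP 16.3.4 says "The WOMAC Composite score is calculated by finding the total of the scores for the 3 subscales", which makes 24 items.

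Neither the SAP nor either protocol version contains a prorating or minimum-items rule. SAP 7.3 imputes missing WOMAC scores only in the sensitivity analyses. The steps in SAP Appendix 3 work on the score and do not use the items answered at the same visit.

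The order of testing in SAP 7.4 is "1) WOMAC pain score, (2) WOMAC physical function score, and (3) WOMAC stiffness score". SAP 16.2.2 sets the model: "The MMRM models for the key secondary efficacy variables will include change from baseline in WOMAC physical function (or stiffness) score" as the repeated outcome. A subject who loses one visit therefore stays in through the others.

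**The concern.** For a given blank rate, an all-items rule costs more the longer the scale, and function is the longest of the three subscales in the fixed sequence. Stiffness can be tested only if function is significant, so lost precision on function also reaches stiffness.

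The discarded answers are the best information about the missing score. Without them, the model predicts the visit from the subject's other visits under missing at random, although 16 of 17 items (94%) may have been observed that day.

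Two further consequences are not about precision. Under SAP 16.3.16 a missing percentage change sets the responder indicator to 0, and the same statistics are produced for physical function. A subject with 16 items showing clear improvement and one blank therefore counts as a non-responder at that visit for every threshold. Under SAP 6.2, baseline is the last non-missing value up to first patch application. WOMAC is given at Screening and at Visit 3 but not at Visit 2 (Protocol 10.2). A blank function item at Visit 3 thus sends the function baseline back to Screening, when subjects are still on stable NSAID therapy (Protocol 8.2.1, criterion 2d). The WOMAC entry criterion concerns pain only, so it does not protect the function baseline.

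**Working it through.** No figure in the plan can be reproduced here. The item non-response rate is not given, and the effect size and sample size behind the 80% power are redacted. The numbers below are illustrations under stated assumptions.

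**Step 1. Share of scores lost.** Inputs: 5, 17 and 24 items (SAP 16.1.1, 16.2.1.1, 16.3.4) and an assumed probability q that an item is blank, independently of the others. The loss is p = 1 − (1 − q)^k.

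**Step 2. Effect on the Week 12 variance for function.** The inflation of the variance of the mean is (1 − R²) × p/(1 − p), where R² is what the other visits explain. The correlation of 0.7 is assumed.
- One earlier visit: R² = 0.7² = 0.49, leaving 51% unexplained.
- Four earlier visits (Weeks 1, 2, 4, 8), equally correlated: R² = 4 × 0.49/(1 + 3 × 0.7) = 1.96/3.1 = 0.63, leaving 37%.

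| q | Pain lost | Function lost | Composite lost | Inflation, one visit | Inflation, four visits |
|---|---|---|---|---|---|
| 0.2% | 1.0% | 3.3% | 4.7% | 1.8% | 1.3% |
| 0.5% | 2.5% | 8.2% | 11.3% | 4.5% | 3.3% |
| 1% | 4.9% | 15.7% | 21.4% | 9.5% | 6.9% |

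Example at q = 1%: p/(1 − p) = 0.1571/0.8429 = 0.186; 0.186 × 0.51 = 9.5% and 0.186 × 0.368 = 6.9%.

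**Step 3. In terms of power.** Assume an effect size of 0.30, which needs 175 per arm for 80% power. With independent blanks at 0.5% and 1%, power falls to 76.7% and 73.1% if the lost subjects contribute nothing, and to 78.8% and 77.5% if the model recovers 60% of the information. If blanks cluster so that 1%, 2% or 5% of visits are affected, power is 79.7%, 79.3% or 78.1% with no recovery at all.

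**Step 4. Error from prorating.** Take k items with equal variance and equal inter-item correlation r, of which m are blank. The error variance as a share of the score variance is m(1 − r)/[(k − m)(1 + (k − 1)r)], for r = 0.4 and 0.6:
- function, one blank: 0.6/(16 × 7.4) = 0.5%; 0.4/(16 × 10.6) = 0.2%;
- function, three blank: 1.8/(14 × 7.4) = 1.7%; 1.2/(14 × 10.6) = 0.8%;
- pain, one of five blank: 0.6/(4 × 2.6) = 5.8%; 0.4/(4 × 3.4) = 2.9%.

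All are well below the 37% to 51% left when the score is predicted from other visits.

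**Step 5. How many lost scores prorating would recover.** The share of lost function scores with exactly one blank is 17q(1 − q)^16/[1 − (1 − q)^17], which is 96% at q = 0.5% and 92% at q = 1%. A minimum of 14 of 17 would keep nearly all of them.

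**The case against.** The rule is prespecified, unambiguous and identical in both arms, and it makes no assumption about the unanswered item. Prorating replaces a missing-at-random assumption about the score with an assumption about the item. WOMAC is administered at clinic visits, where staff can notice a blank, and monitors check that entries are complete (Protocol 14.4.1). The independence assumption spreads blanks over as many visits as possible, and the model recovers part of what is lost.

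Much of this stands, and it limits the size. A reader might infer that Week 12 will lose precision, or that some 16% of function scores will go missing. The documents support neither: they give no rate, and the upper figure needs a 1% blank rate with full independence. A reader might also infer bias or an inflated type I error in the Week 12 comparison; nothing in the documents shows either. Nor does the small error for one blank of 17 justify prorating in general, because for pain it is roughly ten times larger.

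What does not stand is that the matter can be left because blanks will not occur. No passage says that every item must be answered, and SAP 7.3 itself provides for blanks. The responder and baseline consequences are also not softened by the model's use of other visits.

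**Conclusion.** The concern holds as a cheap improvement; it is not a flaw that invalidates the analysis. The all-items rule can discard up to 16 answered items on the first key secondary endpoint. The cost is nil if no item is blank. Under assumed independent blanks of 0.2% to 1% it is about 3% to 16% of function scores per visit, with a Week 12 variance inflation of about 1% to 7% (four earlier visits at correlation 0.7) or 2% to 9.5% (one), and less if blanks cluster. These figures rest on an assumed rate, independence and equal correlations. The actual power loss for function cannot be computed, because the design inputs are redacted and the stated 80% power is not specific to function.

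The non-responder coding and the fallback to a Screening baseline follow from the text whenever a blank occurs. The first holds for SAP 16.3.16; SAP 16.3.10 does not say how a missing score is classed. A reader might also infer that a completer with one blank item would be shifted like a dropout in the sensitivity analyses. That is not settled: SAP 16.1.5 speaks of early discontinuation, while SAP 7.3 and Appendix 3 speak of missing scores or data in general.

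**What to change.** Before unblinding, amend SAP 7.3 and 16.2.1.1:
- Function = 17 × the mean of the answered items when a stated minimum is answered, for example 14 of 17; otherwise missing. The cut-off is a choice to be fixed in advance; the documents do not supply one.
- Replace the integer-or-missing wording in 16.2.1.1, since prorated scores need not be integers.
- Build the composite from the prorated function score.
- Apply the rule at every visit, Visit 3 included, so that the function baseline does not fall back to Screening for a few blank items.
- Keep the all-items rule as a sensitivity check.

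Leave the primary pain score as it is. Prorating it at 4 of 5 items is optional and better kept as a sensitivity analysis, because the error is larger (2.9% to 5.8%) and the primary endpoint's derivation would change.

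The cost is one derivation rule, the related wording and one extra run. The downside is the assumption that a blank item equals the subject's mean of the answered items. If no items are blank, the results are identical.

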16.2.1.2 Second Key Secondary Efficacy Variables and Derivation

The endpoint to address the second Key Secondary Objective is the WOMAC LK3.1 OA (stiffness) change from baseline at Week 12 (Visit 8).

The WOMAC stiffness score is derived by summing the sub-scores for the 2 following items, as collected in the *Western Ontario and McMaster Universities Osteoarthritis Index* eCRF page taking into account missing observations as described in [section 7.3](#):

Each item is rated on a scale of 0 to 4, with 0 being none and 4 being extreme.

Noven Pharmaceuticals, Inc.

Protocol HP-5000-US-07

Statistical Analysis Plan

Page 32 of 58

Therefore, the WOMAC stiffness score, for a specific visit, will be one of the integer values from 0 to 8 or missing.

16.2.2. ANALYSIS OF KEY SECONDARY EFFICACY VARIABLES

The MMRM models for the key secondary efficacy variables will include change from baseline in WOMAC physical function (or stiffness) score as the repeated dependent variable, with effects for treatment (HP-5000 and placebo), visit, treatment-by-visit interaction, and the baseline WOMAC physical function (or stiffness) score as a covariate. Initially an unstructured covariance matrix will be used to model the correlation among repeated measurements within subject.

If the unstructured covariance matrix fails to converge, the same procedure for selection of covariance structures as was specified for the primary efficacy will be done as listed in [section 16.1.3](#). Descriptive and inferential statistics, comparable to those described in [sections 16.1.3 through 16.1.6](#) for the primary efficacy variable will be presented for each of the key secondary efficacy variables.

16.2.3. MULTIPLICITY METHOD FOR PRIMARY AND KEY SECONDARY EFFICACY

The fixed-sequence procedure will be applied for primary and key secondary endpoints as described in [Section 7.4](#). All statistical tests of hypotheses in this analysis will be 2-sided with a Type I Error rate of 0.05.

16.3 OTHER SECONDARY EFFICACY

Other secondary efficacy analyses will be performed for the ITT Set. For each below secondary efficacy variable, tables will be produced that display descriptive and inferential statistics by visit and treatment group. For continuous change from baseline variables descriptive and inferential statistics, comparable to those described in [section 16.1.3](#) for the primary efficacy variable will be presented. With no adjustment for intercurrent events.

For the secondary variables expressed as proportion of subjects with a response that is categorized as binary a logistic regression model will be used to obtain the point estimate of the odds ratio between treatment groups (HP-5000 and placebo) and the associated 95% confidence interval.

16.3.1 WOMAC LK3.1 OA (PAIN) CHANGE FROM BASELINE AT WEEKS 1, 2, 4, AND 8

The change from baseline will be analyzed using a MMRM analysis. As described in [section](#)

Noven Pharmaceuticals, Inc.
Protocol HP-5000-US-07

[16.1.3](#) for the WOMAC pain score, the same MMRM model will be applied.

A plot of the LS Mean change from baseline by visit will be presented.

16.3.2 WOMAC LK3.1 OA (PHYSICAL FUNCTION) CHANGE FROM BASELINE AT WEEKS 1, 2, 4, AND 8

The change from baseline will be analyzed using a MMRM analysis. As described in [section 16.1.3](#) for the WOMAC physical function score, the same MMRM model will be applied.

A plot of the LS Mean change from baseline by visit will be presented.

16.3.3 WOMAC LK3.1 OA (STIFFNESS) CHANGE FROM BASELINE AT WEEKS 1, 2, 4, AND 8

The change from baseline will be analyzed using a MMRM analysis. As described in [section 16.1.3](#) for the WOMAC stiffness score, the same MMRM model will be applied.

A plot of the LS Mean change from baseline by visit will be presented.

16.3.4 WOMAC LK3.1 OA (COMPOSITE SCORE) CHANGE FROM BASELINE AT WEEKS 1, 2, 4, AND 8

The change from baseline will be analyzed using a MMRM analysis. As described in [section 16.1.3](#) for the WOMAC composite score, the same MMRM model will be applied, with no adjustment for intercurrent events. The WOMAC Composite score is calculated by finding the total of the scores for the 3 subscales, WOMAC pain, WOMAC physical function and WOMAC stiffness, and then dividing by 96. Higher scores on the WOMAC indicate worse pain, stiffness, and functional limitations.

16.3.5 CHANGE FROM BASELINE IN PAIN INTENSITY ASSESSED ON AN 11-POINT NRS AT WEEKS 1, 2, 4, 8, AND 12

Change from baseline in pain intensity will be tabulated on an 11-point NRS at Weeks 1, 2, 4, 8, and 12 (visits 4, 5, 6, 7, and 8) average and worst score between baseline and each week. The NRS pain score for assessment at Weeks 1, 2, 4, 8, and 12 (visits 4, 5, 6, 7, and 8) is the mean of the NRS pain scores reported for pain [REDACTED]

[REDACTED] using the 11-point NRS average pain intensity score and NRS worst pain intensity score. Baseline is [REDACTED]

Average pain intensity:

Noven Pharmaceuticals, Inc.

Protocol HP-5000-US-07

Statistical Analysis Plan

Page 34 of 58

Change from baseline in average pain intensity assessed on an 11-point NRS at Weeks 1, 2, 4, 8, and 12 (visits 4, 5, 6, 7, and 8) will be presented descriptively and analyzed similar to the primary analysis of the change from baseline as the repeated variable, with effects for treatment (HP-5000 and placebo), visit, treatment-by-visit interaction, and the baseline average pain intensity score as a covariate. With no adjustment for intercurrent events.

The average pain is collected through eDiary in clinic.

Worst pain intensity:

Change from baseline in worst pain intensity assessed on an 11-point NRS at Weeks 1, 2, 4, 8, and 12 (visits 4, 5, 6, 7, and 8) will be presented descriptively and analyzed similar to the primary analysis of the primary efficacy variable (refer to [Section 16.1.3](#)). A MMRM model will be used with change from baseline as the repeated variable, with effects for treatment (HP-5000 and placebo), visit, treatment-by-visit interaction, and the baseline worst pain intensity score as a covariate. With no adjustment for intercurrent events.

The worst pain is collected through eDiary in clinic.

A figure plotting the 3-day average of the average and worst NRS pain scores by visit will be generated.

16.3.6 CHANGE FROM BASELINE IN PAIN INTENSITY ASSESSED ON AN 11-POINT NRS OF A WEEKLY AVERAGE OF ALL AVAILABLE DAILY PAIN SCORES AT EACH WEEK FROM WEEK 1 THROUGH 12

Change from baseline to each week (Week 1 through 12) in pain intensity will be assessed on an 11-point NRS of a weekly average of all available daily pain scores at each week.

All available scores of daily NRS scores evaluated when the subjects replace the patch and the NRS scores evaluated before any rescue medication use will be included. Weekly pain would be the mean of average NRS pain and mean of worst NRS pain over 7 days (e.g., Week 1 = average pain scores on Days 1 through 7). Baseline is defined 

A weekly average of all available daily pain scores will be calculated from subject's diaries. MMRM model will be used with change from baseline as the repeated variable, with effects for treatment (HP-5000 and placebo), visit, treatment-by-visit interaction, and the baseline 3-day average NRS score as a covariate. With no adjustment for intercurrent events.

A figure plotting the weekly average of the average and worst NRS pain scores by week will be generated.

Noven Pharmaceuticals, Inc.

Protocol HP-5000-US-07

16.3.7 CHANGE FROM BASELINE IN PATIENT GLOBAL ASSESSMENT (PGA) AT WEEKS 1, 2, 4, 8, AND 12

Subject's will be asked to complete the following statement: "How would you rate your osteoarthritis condition over the last 24 hours?" using a 5-point scale from 0 (Very Good) to 4 (Very Poor).

Change from baseline in PGA at Weeks 1, 2, 4, 8, and 12 (visits 4, 5, 6, 7, and 8) will be analyzed similar to the primary analyses (refer to [section 16.1.3](#)). An MMRM model will be used with change from baseline in PGA as the repeated dependent variable, with effects for treatment (HP-5000 and placebo), visit, treatment-by-visit interaction, and the baseline PGA score as a covariate. With no adjustment for intercurrent events. The observed value and change from baseline will also be summarized descriptively by visit using summary statistics in addition to the above noted model.

The responders are defined as subjects achieving a score of

0: Very Good or

1: Good

Non-responders are defined as subjects achieving a score of

2: Moderate or

3: Poor or

4: Very Poor

[figure not shown]
Subjects not assessed will be considered as having missing data.

The proportion of PGA responders and non-responders will be summarized by visit. Treatment comparisons will be made using a logit model adding PGA baseline as the covariate. This model will present an estimate of the odds ratio, Wald 95% CI, and p-value. The sample SAS code used for the Logit model for the PGA analysis can be found in [Appendix 2](#).

16.3.8 PATIENT GLOBAL IMPRESSION OF CHANGE (PGIC) AT WEEKS 1, 2, 4, 8, AND 12

Subject's will be asked the following question: "How would you rate your overall improvement with treatment during the clinical trial?" using a 7-point scale from 1 (Very Much Improved) to 7 (Very Much Worse).

PGIC at Weeks 1, 2, 4, 8, and 12 (visits 4, 5, 6, 7, and 8) will be analyzed using logit model as

Noven Pharmaceuticals, Inc.

Protocol HP-5000-US-07

Statistical Analysis Plan

Page 36 of 58

below.

The responders are defined as subjects achieving a score of

- 1: Very much improved or
- 2: Much improved

Non-responders are defined as subjects achieving a score of

- 3: Minimally improved
- 4: No change or
- 5: Minimally worse or
- 6: Much worse or
- 7: Very much worse

Subjects achieving a score of 0: Not assessed will be considered as having missing data.

The proportion of PGIC responders and non-responders will be summarized by visit. Treatment comparisons will be made using a logit model with treatment effect as the only term in the model analyzing the proportion of PGI responders. For each comparison, an estimate of the odds ratio, corresponding Wald 95% CI, and p-value will be presented. The observed values will also be summarized descriptively by visit using summary statistics.

